1.3 STUDY RATIONAL AND BENEFIT-RISK ASSESSMENT

Seasonal influenza is a major burden to global health. There are an estimated 3–5 million cases of severe disease worldwide and approximately 290–650 thousand people die from influenza annually (WHO 2017a, WHO 2018, Baxter 2016). Influenza also places significant demands on healthcare services each season, and impacts society through lost workforce productivity (WHO 2018). Influenza virus infection can be especially severe in stem cell transplant (SCT) recipients. In these patients the clinical course is often prolonged with a higher frequency of progression of the disease to the lower respiratory tract, protracted viral shedding and increased death^{1,2}. Neuraminidase inhibitors (NAI), including oseltamivir, are the mainstay of influenza therapy. However, because the paucity of initial symptoms and the frequent absence of fever^{3,4} the diagnosis of influenza is often delayed in this population, and treatment with NAI is often started later than 48-hours after the onset of influenza, that is the period during which NAI

treatment is most effective. Moreover, while low rates of NAI resistance are reported in the general population, high viral replication associated with prolonged therapeutic courses favor the rapid emergence and transmission of NAI-resistant influenza in SCT recipients⁵.

Baloxavir (XofluzaTM) is a first-in-class influenza antiviral that blocks influenza virus RNA replication by inhibiting cap-dependent endonuclease activity (Omoto *et al* 2018). Baloxavir has a prolonged half-life allowing the administration in single dosing and it was recently approved for use in the US for the treatment of uncomplicated influenza. In the Phase III CAPSTONE-1 double-blind randomized study in otherwise healthy patients (Hayden *et al* 2018), a single treatment of baloxavir (40 mg for patients <80 kg and 80 mg for patients ≥80 kg) significantly reduced the time to alleviation of symptoms compared with placebo and also effectively reduced viral load, as shown by a significant reduction compared with placebo in:

- The proportion of patients with positive influenza titer between Days 2 and 5
- The proportion with positive influenza virus RNA determined by PCR on Day 5
- The median time to cessation of viral shedding

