Participants will assess the severity of 7 influenza-associated symptoms (cough, sore throat, headache, nasal congestion, feverishness/chills, muscle/joint pain, and fatigue) on a 4-point scale (0 = no symptoms, 1= mild, 2 = moderate, and 3 = severe) as specified in section 4.5.7. Improvement is defined as: improvement pre-existing symptoms (i.e cough, fatigue, or muscle/join pain that existed prior to influenza) that were worse at baseline and improve at least 1 point from baseline; pre-existing symptoms not worse at baseline that maintain baseline severity; and new symptoms that are alleviated, defined as a symptom score of non (0) or mild (1).

Once all patient's influenza symptoms are alleviated, maintained, or improved (hereafter all will be called 'improvement') as defined above, the endpoint will be reached.

6. **Percentage of patients who experience each influenza-related complication** (hospitalization, death, sinusitis, otitis media, bronchitis, and radiologically-confirmed pneumonia) as an adverse event after the initiation of study treatment symptoms [symptoms [Time Frame: From Day 1 pre-treatment up to Day 30].
7. **Time to Return to Preinfluenza Health Status** [Time Frame: From Day 1 pre-treatment up to Day 30]. Participants will be asked to record their preinfluenza health status on a scale from 0 (worst possible health) to 10 (normal health [for someone same age and condition]), and their health status at baseline and every day after initiation of study treatment on the same scale as specified in section 4.5.7. Return to preinfluenza health status is defined as time from the initiation of the study treatment to the first time when the health status score was equal to or higher than the preinfluenza health status score.
8. **Time to viral clearance**, as assessed by difference in Percentage of Participants Positive by Influenza plaque assay and qPCR at each time-point (in each treatment group) The definition of the time to sustained cessation of infectious virus detection is the time

between the start of treatment and when virus titer remained below the detection limit on all subsequent sampling time points.

9. Measure treatment-emergent variants of neuraminidase and polymerase known to confer antiviral resistance to oseltamivir in each arm by direct next-generation sequencing symptoms [Time Frame: From Day 1 pre-treatment up to Day 30]

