4.1.1 INCLUSION CRITERIA

Patient must meet the following criteria for study entry:

- Adult patients: Signed informed consent by any patient capable of giving consent, or, where the patient is not capable of giving consent, by his or her legal/authorized representative
- Age \geq 18 years at the time of signing the Informed Consent Form/Accent Form
- Ability to comply with the study protocol, in the investigator's judgment
- Be defined as immunocompromised*, as defined by:
 1. Have received allogeneic bone marrow transplant, or
 2. Is currently receiving treatment with chemotherapy and/or CAR-T cell therapy for hematologic malignancies (e.g., leukemia, myeloma, lymphoma), or

- 3. Received treatment with chemotherapy and/or CAR-T cell therapy for hematologic malignancies (e.g., leukemia, myeloma, lymphoma) within the past 1 year.
- Tested positive for influenza infection after the onset of symptoms using a polymerase chain reaction (PCR)-based diagnostic assay.
- Presence of (a) fever ($\geq 38.0^{\circ}\text{C}$ per tympanic or rectal thermometer; $\geq 37.5^{\circ}\text{C}$ per axillary, oral or forehead/temporal thermometer) or (b) any influenza symptoms (cough, sore throat, nasal congestion, headache, feverishness or chills, muscle or joint pain, fatigue).
- The time interval between the diagnosis of influenza and the pre-dose examinations is 48 hours or less.
- For women of childbearing potential: Agreement to remain abstinent (refrain from heterosexual intercourse):

Women must remain abstinent or use contraceptive methods with a failure rate of $< 1\%$ per year during the treatment period and for 28 days after the last dose of study treatment.

Hormonal contraceptive methods must be supplemented by a barrier method.

A woman is considered to be of childbearing potential if she is postmenarcheal, has not reached a postmenopausal state (≥ 12 continuous months of amenorrhea with no identified cause other than menopause), and has not undergone surgical sterilization (removal of ovaries and/or uterus).

Examples of contraceptive methods with a failure rate of $< 1\%$ per year include bilateral tubal ligation, male sterilization, hormonal contraceptives that inhibit ovulation, hormone-releasing intrauterine devices, and copper intrauterine devices.

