4.1.2 EXCLUSION CRITERIA

Patients who meet any of the following criteria will be excluded from study entry:

- Patients who have received more than 48 hours of antiviral treatment for the current influenza infection prior to screening
- Patients who have received Baloxavir for the current influenza infection
- Known contraindication to neuraminidase inhibitors
- Patients weighing < 40 kg

- Patients unable to swallow tablets
- Patients with known severe renal impairment (estimated glomerular filtration rate $< 30 \text{ mL/min}/1.73 \text{ m}^2$) or receiving continuous renal replacement therapy, hemodialysis, peritoneal dialysis
- Patients with any of the following laboratory abnormalities detected within 24 hours prior to or during screening (according to local laboratory reference ranges):
 - ALT or AST level > 5 times the upper limit of normal (ULN)
OR
 - ALT or AST > 3 times the ULN and total bilirubin level > 2 times the ULN
- Pregnant or breastfeeding, or positive pregnancy test in a predose examination, or intending to become pregnant during the study or within 28 days after the last dose of study treatment
- Exposure to an investigational antimicrobial within 5 half-lives or 30 days (whichever is longer) of randomization
- Any serious medical condition or abnormality in clinical laboratory tests that, in the investigator's judgment, precludes the patient's safe participation in and completion of the study
- Known hypersensitivity to baloxavir marboxil or the drug product excipients
- Known COVID-19 coinfection
- Unwilling to undergo nasopharyngeal (NP) swabs as per study schedule

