4.5.7 SELF ASSESSED MEASUREMENTS

1. TIME TO SYMPTOMS IMPROVEMENT

This is defined as time from the start of treatment to patient reported improvement in all seven influenza-associated symptoms for a duration of at least 24 hours. Symptoms that were present before the development of influenza symptoms will have to improve by at least one level. If patient was not experiencing any symptom, all symptoms will have to be rated as mild or absent. Patients will be given a diary to self-assess daily the severity of the following influenza-associated symptoms on a 4 points scale, at baseline and then for the first 15 days of the study.

	Date			
	No symptoms Score 0	Mild symptoms Score 1	Moderate symptoms Score 2	Severe symptoms Score 3
cough				
sore throat				
headache				
nasal congestion				
feverishness				
chills				
muscle or joint pain				

At baseline (i.e., the predose examinations), patients will be asked if preexisting symptoms existed (within the last 30 days) and if they were worsened by influenza. Patients will be asked to rate the severity at baseline that needs to improve. The modification for preexisting symptoms will be done as follows (ISON et al 2020, DOI:[https://doi.org/10.1016/S1473-3099\(20\)30004-9](https://doi.org/10.1016/S1473-3099(20)30004-9))

A. Symptoms that existed prior to developing influenza that are judged by the patient to be **worse at baseline** (before therapy) must improve from baseline severity

o Improvement in baseline severity is defined as follows:

Severe to moderate, mild, or absent

Moderate to mild or absent

Mild to mild or absent

Absent to mild or absent

B. Symptoms that existed prior to developing influenza that were judged by the patient to **NOT be worse at baseline** (before therapy) must have their baseline severity maintained

o Maintenance of baseline severity is as follows:

Severe is defined as severe or less than severe

Moderate is defined as moderate or less than moderate

Mild is defined as mild or absent

Absent is defined as mild or absent

- For **new symptoms at baseline** (before therapy), alleviation of symptoms assessment must be achieved

- o Alleviation of symptoms is defined as follows:

Severe is mild or absent

Moderate is mild or absent

Mild is mild or absent

Absent is mild or absent

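### Time to symptom improvement (secondary endpoint 5) rests on improvement rules that contradict each other, and it counts patients with only mild new symptoms as improved before the first dose

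*Combined protocol and SAP*

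**What the plan says.** Section 4.1.1 admits patients with fever or "any influenza symptoms (cough, sore throat, nasal congestion, headache, feverishness or chills, muscle or joint pain, fatigue"), without a severity threshold. Its time limit runs from diagnosis, not from symptom onset: "The time interval between the diagnosis of influenza and the pre-dose examinations is 48 hours or less". Section 4.1.2 excludes only "Patients who have received more than 48 hours of antiviral treatment for the current influenza infection prior to screening", so shorter prior treatment is allowed. Section 1.3 says diagnosis is often late in this population "because the paucity of initial symptoms and the frequent absence of fever".

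Secondary endpoint 5 is reached when every symptom meets its rule for at least 24 hours. Section 2.1 gives three rules:
- a pre-existing symptom made worse by influenza must fall by at least one point;
- a pre-existing symptom not made worse must hold its baseline level;
- the third class is "new symptoms that are alleviated, defined as a symptom score of non (0) or mild (1").

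Section 4.5.7 states the rules again. Its opening says: "Symptoms that were present before the development of influenza symptoms will have to improve by at least one level". Rule A, for worsened pre-existing symptoms, includes "Mild to mild or absent". Rule B, for those not worsened, asks only for maintenance. The list for new symptoms includes "Mild is mild or absent". Patients who do not improve are censored at their last observation.

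Statistical Considerations plans Kaplan-Meier estimates per arm and a generalized Wilcoxon comparison. It calls the between-arm comparisons exploratory and offers the per-arm summaries for planning later studies. It defines an analysis set for the primary endpoint but none for this one.

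**The concern.** There are two problems.

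First, the definition is not unique. The same diary can give an event under one statement of the rule and a censored time under another, so two analysts who both follow the plan could report different Kaplan-Meier curves.

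Second, some patients may have nothing left to improve when treatment starts. They become early events for a reason unrelated to treatment, and no section handles them separately. The per-arm medians would then describe an unlabelled mix of patients who were already improved and patients who were still symptomatic, although those medians are meant to inform future trials. Equal early events in both arms would also dilute any real difference between them.

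**Working it through.** **The rules side by side.** Assume every other symptom meets its rule.

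| Symptom and course | Section 2.1 | 4.5.7 opening | 4.5.7 lists |
|---|---|---|---|
| Pre-existing, worsened, mild at baseline, stays mild | not improved | not improved | improved (rule A) |
| Pre-existing, not worsened, moderate, stays moderate | improved | not improved | improved (rule B) |
| New, mild at baseline, stays mild | improved | improved | improved |

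Row 1 is an event or a censored time depending on the section used. Row 2 conflicts only if the opening is not replaced by rules A and B. Row 3 has no conflict, but the patient is in the improved state before dosing and needs only 24 hours without worsening.

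**Effect on the medians.** The plan states no median, event count or power for this endpoint, so there is no figure of its own to reproduce. Inputs:
- 15 patients per arm (Statistical Considerations).
- Share m of mild-only patients: not in the documents; assumed 10%, 20%, 30% (3, 6, 9 of 30).
- Median in the other patients: 81.0 h, borrowed from the oseltamivir arm of the high-risk phase 3 trial in Section 1.2.1.1. This is an assumption about a different population.
- All mild-only patients stay mild for 24 hours (the extreme case).

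If F is the time distribution in the other patients, the arm median t solves m + (1 - m)F(t) = 0.5. Let k = ln(2(1 - m))/ln 2, which is 0.848, 0.678, 0.485. Then:
- Exponential from hour 0: t = 81.0 × k.
- Exponential shifted by 24 h, same median: t = 24 + (81.0 - 24) × k.
- Weibull with shape 2: t = 81.0 × √k.

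| m | Exponential | Shifted exponential | Weibull, shape 2 | Factor on 81.0 h |
|---|---|---|---|---|
| 10% | 68.7 h | 72.3 h | 74.6 h | 0.85-0.92 |
| 20% | 54.9 h | 62.7 h | 66.7 h | 0.68-0.82 |
| 30% | 39.3 h | 51.7 h | 56.4 h | 0.49-0.70 |

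All these medians exceed 24 h, so with the other patients' times held fixed, placing the mild-only events at 0 h or at 24 h gives the same median.

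If half of the mild-only patients worsen and then behave like the rest, the effective share halves to 5%, 10%, 15%. The exponential factors become ln(1.9)/ln 2 = 0.926, ln(1.8)/ln 2 = 0.848 and ln(1.7)/ln 2 = 0.766.

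**Effect on the exploratory contrast.** This depends on the true effect.
- For the cited medians of 73.2 h (baloxavir alone) and 81.0 h (oseltamivir alone), simulated power at m = 30% is 6% with all patients and 6% in the restricted set. That is close to the 5% level, so this contrast could not show a loss.
- With an assumed hazard ratio of 2.5 in the other patients (24 h-shifted exponential, control median 81.0 h, mild-only events at 24 h, 15 per arm, 10,000 runs):

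| m | Power, all patients | Power, restricted set |
|---|---|---|
| 0% | 55% | 55% |
| 10% | 37% | 49% |
| 20% | 25% | 43% |
| 30% | 17% | 39% |

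In the same runs at m = 20%, the average arm medians are 65.1 and 40.4 h with all patients (gap 24.7 h), against 84.2 and 48.2 h in the restricted set (gap 36.0 h).

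**The case against.** - **Severity at entry.** Section 1.3 also says influenza can be especially severe in transplant recipients, and Section 3.3.1 calls their disease severe and prolonged. The remark about few initial symptoms explains late diagnosis; it does not describe severity at the first dose. This stands: mild-only patients are possible under the entry rules, but their number is unknown.
- **The rule looks deliberate.** Section 4.5.7 lists mild and absent baseline scores explicitly. That is fair, but a deliberate rule still needs a stated way to report patients who meet it before dosing.
- **Order of reading.** Section 2.1 refers to 4.5.7, where the opening sentence is followed by rules A and B as the stated modification for pre-existing symptoms. On that reading the conflict between the opening and rule B largely disappears. The conflict between Section 2.1 and rule A does not, because Section 2.1 spells out its own one-point fall and nothing says which text prevails.
- **Target population.** The all-patient median is the right planning figure for a later trial with the same entry rules and endpoint. This stands. A reader might infer that the restricted set should become the main analysis, but the documents do not settle that. It would change the population described and leave out mild-only patients who later worsen.

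**Conclusion.** The point holds and is minor. The contradiction between Section 2.1 and rule A needs no assumption about case mix. The shortening of the medians follows from the text in direction only. Its size rests on an assumed share, a borrowed 81.0 h median, the shape of the time distribution, and all mild-only patients staying mild.

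Three stronger readings are not supported:
- That the medians will be about halved. The factor 0.49 needs a 30% share, exponential times from hour 0 and no worsening; other shapes with the same median give 0.64 to 0.70.
- That the comparison between arms is biased or its type I error inflated. The rule is the same in both arms and the mild-only status is fixed before dosing.
- That the loss of power is known to be large, or known to be negligible. It is near zero for the cited 73.2 v 81.0 h and substantial at a hazard ratio of 2.5, and the documents give no expected effect on this endpoint.

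The viral-load co-primaries are not touched.

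**What to change.** 1. Use one improvement rule in Section 2.1, the opening of Section 4.5.7, and rules A and B. In particular, settle whether a worsened mild symptom that stays mild counts as improved.
2. State whether the event time is the start or the end of the 24 hours.
3. Keep the all-patient analysis. Alongside it, report the Kaplan-Meier estimates and the Wilcoxon contrast in patients with at least one symptom that does not meet its criterion at the pre-dose assessment. Give the number per arm who already met every criterion.

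The cost is wording in the protocol and analysis plan. The pre-dose scores and the pre-existing-symptom questions are already collected under Section 4.5.7, and restricting on them uses no post-randomization outcome. The downside is a smaller set (15 × 0.7 = 10.5, so about 10 to 11 per arm at a 30% share) that describes a narrower population. That is the reason to report both sets.

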2. OBJECTIVES AND ENDPOINTS

2.1 PRIMARY OBJECTIVE

The primary objective is to evaluate the efficacy of both the combination therapy of baloxavir with oseltamivir and that of oseltamivir plus placebo in SCT patients with influenza as measured by changes in influenza viral RNA loads at day 10 from baseline (day 1) and compare between arm differences in decline of viral load

The co-primary efficacy endpoints are:

- Change of influenza viral RNA loads from baseline (day 1) at the end of treatment (day 10) as measured by quantitative real time polymerase chain reaction (qRT-PCR, nucleic acid).
- Between-treatment-arm difference in the change of influenza viral RNA loads from baseline (day 1) at the end of treatment (day 10) as assessed by quantitative real time polymerase chain reaction as measured by (qRT-PCR, nucleic acid) and by Influenza plaque assay (replicating virus).

The secondary efficacy endpoints are:

1. **Change of influenza viral RNA load from baseline (day 1) at day 4 and day 7 and 10** as measured by quantitative real time polymerase chain reaction (qRT-PCR, nucleic acid) in each treatment arm.
2. **Difference in change of influenza viral loads from baseline (day 1) at day 4, 7 and 10 between the two treatment arms** as measured by quantitative real time polymerase chain reaction (qRT-PCR, nucleic acid)
3. **Change of influenza viral loads from baseline (day 1) at day 4, 7 and 10** as measured by Influenza plaque assay (replicating virus) in each treatment arm.
4. **Difference in change of influenza viral loads from baseline (day 1) at day 4, 7 and 10 between the two treatment arms** as measured by Influenza plaque assay (replicating virus).
5. **Time to Improvement of Individual Influenza Symptoms** [Time Frame: From Day 1 pre-treatment up to Day 30] defined as the time from the initiation of the study treatment to the improvement of influenza symptoms as assessed by patient-reported outcome measures on a single scale as specified in section 4.5.7. Time to improvement of symptoms is defined as the time from the start of treatment to the time when each of the influenza symptoms will be alleviated, maintained, or improved, for a duration of at least 24 hours.

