4.5.5 INFLUENZA DIAGNOSTIC TEST

For patients to be eligible for this study, a RT-PCR is required to be performed to inform a diagnosis of influenza. If a site has performed a RT-PCR test within the 24 hours prior to screening, the local RIDT or RT-PCR result can be used. Screening test for COVID-19 will also be performed before enrollment.

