For secondary viral loads related endpoints, summary statistics in terms of mean, standard deviation, median and range will be calculated for each arm at each time points among patients with relevant measurements. Longitudinal analyses using mixed effects repeated measures will be used to model the mean viral loads overall time. Contrasts of interest including between arm differences will be explored using simultaneous tests of general linear hypotheses. If normality is a concern, log-transformed and standardized viral load data will be used. Longitudinal analysis will be carried out among patients with at least one relevant viral load measurement. Kaplan-Meier estimates will be generated for time to events endpoints such as time to Improvement of Individual Influenza Symptoms, the time to viral clearance and time to return to preinfluenza health status for each study arm. Between study arm difference in these endpoints will be explored using the generalized Wilcoxon test.

Categorical data such as the occurrence of treatment-emergent variants of neuraminidase and polymerase by direct next-generation sequencing and AE's will be summarized in terms of counts and proportions separately for each arm.

Between arm difference in the categorical variable will be explored using Fisher's exact test. The study is likely will not have adequate power to detect between arm differences and all the between arms comparisons are considered exploratory. Summary statistics generated for study endpoints for each arm will provide useful information for planning future studies.

The power calculations were performed using PASS 15 Power Analysis and Sample Size Software (2017). NCSS, LLC. Kaysville, Utah, USA, ncss.com/software/pass. All comparisons will be two-tailed, with a significance level at 0.05 and 95% confidence intervals will also be reported. All analyses will be performed in SAS Version 9.4 (2019), SAS Institute, Inc., Cary, NC; and R Version 4.0.4 (2021).

Note: The statistical considerations section was written by [name], MS, and revised by [name], in the Division of Biostatistics, Department of Population Health Sciences, Weill Cornell Medicine.

Influenza sequence analysis will be performed by [name], Director of Systems Genomics Section at the Laboratory of Parasitic Diseases of NIAID/NIH and expert in Influenza evolution.

No interim analysis is planned for this study

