- g. Perform assessments at any unscheduled visits based upon clinician's discretion.
- h. During the study treatment period (Day 1/Visit 1 to Day 10), all vital sign measurements (i.e., respiratory rate, pulse rate, peripheral oxygen saturation, systolic and diastolic blood pressures, and body temperature) should be recorded when on-site. For all other visits, the only vital signs measurement taken will be temperature. After day 10 vital sign measurements and specific assessments are to be recorded at the investigators' discretion (e.g., if symptoms and signs persist during follow-up).
- i. Presence or absence and type of respiratory support; oxygen saturation.
- j. See Section X for tests included in laboratory panels.

- k. Liver function test results to be reviewed by the investigator before Xofluza, or its matching placebo, is administered. On Day 1, prior blood results if tests conducted within 24 hours prior to screening. On Day 4 and day 7, blood liver chemistry panel should be reviewed before the patient will receive Xofluza or matching placebo on this study day.
 - l. Nasopharyngeal swabs for RT-PCR: RT-PCR for influenza and covid-19 should be performed at screening.
 - m. If a chest X-ray has not been taken within the 24 hours prior to screening, it will be performed per clinical provider decision. If the SOC is a chest CT scan, this can be used as alternative to the chest X-ray per clinical provider decision.
 - n. All women of childbearing potential will have a pregnancy test at screening (urine or serum).
 - o. Self-assessment of seven influenza-associated symptoms (cough, sore throat, headache, nasal congestion, feverishness or chills, muscle or joint pain, and fatigue) on a four-point scale (with 0 indicating no symptoms, 1 mild symptoms, 2 moderate symptoms, and 3 severe symptoms) twice daily from enrolment (day 1) until day 9 and once daily on days 10–15, and record their results in the patient diary.
 - p. Baloxavir treatment or Baloxavir-matched placebo dosing will occur on Day 1 and Day 4, with a further dose at Day 7
 - q. The SOC NAI (Oseltamivir) will be administered from Day 1 through Day 10.

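### The plaque-assay endpoints include patients with no detectable replicating virus on the Day 1 swab, which pulls the between-arm comparison towards no difference

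*Combined protocol and SAP*

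**What the plan says.** **Entry.** Section 4.1.1 requires "Tested positive for influenza infection after the onset of symptoms using a polymerase chain reaction (PCR)-based diagnostic assay". Neither 4.1.1 nor 4.1.2 limits the time since symptom onset. Section 4.1.2 excludes "Patients who have received more than 48 hours of antiviral treatment for the current influenza infection prior to screening", so up to 48 hours of prior treatment is allowed.

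**Endpoints.** In Section 2.1 the second co-primary endpoint is the between-arm difference in change from Day 1 to Day 10, "as measured by (qRT-PCR, nucleic acid) and by Influenza plaque assay (replicating virus". Secondary endpoints 3 and 4 are plaque-assay changes at Days 4, 7 and 10, within and between arms. Endpoint 8 is time to viral clearance, assessed through the percentage positive by plaque assay and qPCR at each time point. It defines time to sustained cessation as that "between the start of treatment and when virus titer remained below the detection limit on all subsequent sampling time points".

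**Analysis sets.** Statistical Considerations defines the modified intention-to-treat set by having measurements at both baseline and Day 10. For the secondary loads: "Longitudinal analysis will be carried out among patients with at least one relevant viral load measurement". The abbreviation list mentions an influenza-infected mITT, but nothing ties it to a Day 1 titre. Clearance times are to be compared by the generalized Wilcoxon test.

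**Age of the qualifying PCR.** There are three statements:
- Section 4.1.1: "The time interval between the diagnosis of influenza and the pre-dose examinations is 48 hours or less".
- Section 4.5.5, on accepting an earlier result: "If a site has performed a RT-PCR test within the 24 hours prior to screening".
- Appendix 1, footnote l: "RT-PCR for influenza and covid-19 should be performed at screening".

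**The concern.** The protocol itself separates RNA (nucleic acid) from plaque assay (replicating virus), and a patient can have the first without the second. Two features make a plaque-negative Day 1 swab plausible here: permitted prior antiviral treatment, and late presentation, since Section 1.3 says diagnosis is often delayed in this population.

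A patient below the plaque limit at Day 1 cannot show a fall in titre. If that patient stays below the limit, the change is zero in either arm. On a literal reading of endpoint 8, clearance falls at the start of treatment. Such patients pull the between-arm difference towards zero. They also shorten the per-arm clearance times, and Statistical Considerations offers the per-arm summaries as its main product for planning later studies.

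The choice of population should not wait. Section 4.2.1 places the virology at the end of the clinical period, and Section 4.3 unblinds once the last patient has completed follow-up.

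**Working it through.** **1. The plan's own figure.** Inputs from Statistical Considerations: 15 per arm, two-sided 0.05, 80% power, detectable difference 1.1 SD. The two-sample noncentral t has noncentrality d√(n/2) on 2n − 2 degrees of freedom. At d = 1.1 and n = 15 the power is 0.828. The effect detectable with 80% power is 1.06 SD by t-test, or 1.09 SD with the Wilcoxon efficiency of 0.955. Both round to 1.1, so the figure reproduces.

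**2. Assumptions.** The plan gives no plaque-titre inputs, so all of these are assumed:
- a share f in each arm is plaque-negative at Day 1 and stays negative (change 0);
- among titre-positives the change is N(−1.5, 1.5²) in control and N(−3.15, 1.5²) in the combination arm, a difference of 1.65 = 1.1 × 1.5;
- the changes are compared by t-test.

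**3. Dilution of the difference.** The mean difference becomes (1 − f) × 1.65, which is 1.485, 1.32 and 0.99 at f = 10%, 20% and 40%. The variance in an arm with mean change μ becomes (1 − f)s² + f(1 − f)μ². At f = 20%:
- control: 0.8 × 2.25 + 0.16 × 2.25 = 2.16, SD 1.47;
- combination: 0.8 × 2.25 + 0.16 × 9.9225 = 3.39, SD 1.84;
- standardised effect: 1.32 / √((2.16 + 3.39)/2) = 0.79, down from 1.1.

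**4. Power for the titre change.** The first column is simulated. The second is the noncentral t at the expected 15(1 − f) per arm. Repeat simulations differ by about one or two percentage points.

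| f | Everyone included | Positives only (expected n per arm) |
|---|---|---|
| 0 | 83% | 83% (15) |
| 10% | 68% | 78% (13.5) |
| 20% | 55% | 73% (12) |
| 40% | 33% | 59% (9) |

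**5. Dependence on the control change.** At f = 20% with everyone included, power is about 70% if the control change is 0, 55% if it is −1.5 and 39% if it is −3. The positives-only figure stays near 73%. Restriction did at least as well in every case tried, but its advantage runs from about 3 to 34 points.

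**6. Time to clearance.** Assume that titre-positives clear by Days 4/7/10 in 20/50/75% (control) and 60/85/95% (combination). Gehan-Wilcoxon power is 72% with no baseline-negatives. With negatives entered as events at time zero it is 50%, 34% and 14% at f = 10%, 20% and 40%. With them excluded it is 67%, 61% and 48%.

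**7. Per-arm medians.** If negatives count at time zero, the reported median is the (0.5 − f)/(1 − f) quantile among true shedders: 0.4/0.9 = 44th percentile, 0.3/0.8 = 37.5th and 0.1/0.6 = 17th at f = 10%, 20% and 40%.

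**The case against.** **Time zero is not stated.** A reader might infer that the plan counts baseline-negative patients as cleared at time zero. It does not say so. That is the literal reading, and it applies only to patients negative on every later sample. Cessation of detection may presuppose detection, and the event could instead be dated to the first later visit. This stands: for endpoint 8 the defect is a missing rule.

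**Baseline-negatives are not uninformative.** A titre can rise later, and preventing a rise is a benefit. If, at f = 20%, half of control negatives but only 10% of combination negatives rose by 3 log10, the difference would be 1.32 + 0.2 × (1.5 − 0.3) = 1.56, not 1.32. So shrinkage by exactly f holds only if negatives stay negative, and the all-patient result should be kept.

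**The age of the PCR is not the mechanism.** It is tempting to blame a result that may be 48 hours old. Section 4.5.5 and Appendix 1 conflict with that figure, and a fresh PCR would not show replicating virus either.

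**The share may be small.** Sections 1.3 and 3.3.3 describe prolonged shedding after transplant. That is fair but indirect, because 4.1.1 also admits non-transplant patients. If f is near zero, the restriction costs almost nothing.

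**Limited consequence.** The plan labels all between-arm comparisons exploratory and concedes low power. It also plans mixed models for the secondary loads, where the simulation used a t-test. The RNA endpoints are little exposed. All of this stands and limits the weight of the point. It does not answer the effect on the per-arm plaque summaries.

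**Conclusion.** The concern holds for the plaque-assay analyses only: secondary endpoints 3, 4 and 8, and the plaque component of the second co-primary. As written, these include patients without detectable replicating virus at Day 1. Those who stay negative draw the comparison towards no difference and can shorten the reported clearance times.

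The direction follows from the definitions. The size does not, because the documents give neither the baseline-negative share nor any plaque-titre planning values. The power figures are illustrations that rest on an effect size borrowed from the plan's general viral-load statement, an assumed control change, and negatives staying at zero.

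The documents do not support extending the point to the RNA co-primary analysis, reading time zero as a stated rule, or treating any one power loss as an estimate for this trial.

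**What to change.** In Section 2.1 and Statistical Considerations:

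- State that the plaque-assay analyses of secondary endpoints 3, 4 and 8, and the plaque component of the second co-primary, use patients with a titre at or above the detection limit on the Day 1 pre-dose swab.
- Give the all-patient result as a supportive analysis, so that patients who turn positive later are not lost. State there how endpoint 8 treats a patient already below the limit at Day 1.
- Report the number of baseline-negative patients by arm. With 15 per arm, a chance imbalance could bias the all-patient comparison in either direction.

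Eligibility, randomisation, sampling and the RNA co-primary analysis stay unchanged. The Day 1 titre is already needed for the planned changes from baseline. It is a pre-treatment value, so the restricted comparison remains randomised. A plaque-positive entry criterion would not fit, because the assays are run on frozen samples after the clinical period. The cost is wording and a smaller denominator: 15 × 0.8 = 12 per arm at f = 20%, or 15 × 0.6 = 9 at 40%.

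Separately, the three statements on the timing of the qualifying PCR (4.1.1, 4.5.5 and Appendix 1 footnote l) must be reconciled.
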